8.2 Intraoperative Complications

An intraoperative complication will be limited to any issue arising from the time the patient enters the operating room until the time that the patient leaves the operating room. Intraoperative complications are defined as instances where the anesthesia or surgical team alter treatment or surgical management to address an issue. All intraoperative complications documented by the anesthesia or surgical teams in the electronic medical record will be collected and their severity classified using the CLASSIC scale below¹⁴.

CLASSIC Grade	Definition
Grade 0	No deviation from the ideal intraoperative course
Grade 1	Any deviation from the ideal intraoperative course without the need of any additional treatment or intervention
Grade 2	Any deviation from the ideal intraoperative course with the need of any additional treatment or intervention not life-threatening and not leading to permanent disability
Grade 3	Any deviation from the ideal intraoperative course with the need of any additional treatment or intervention life-threatening and/or leading to permanent disability
Grade 4	Any deviation from the ideal intraoperative course with death of the patient

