Adverse Events ^f	X	X	X
Intraoperative Complications ^g		X	
Postoperative Complications ^g		X	X
Prior and Concomitant therapy	X	X	
Pharmacokinetic data			
PK sample collection			
Plasma sample collection		X	
Intestine sample collection		X	

a: Demographics to be included: gender, date of birth, age, race, comorbidities, gestational age at birth and birth weight

b: May be obtained through review of electronic medical record. All assessment or laboratory collections performed as standard of care only. No assessments or blood draws other than PK data are performed solely for the purposes of this study

c: Vital signs to be included: weight, height, heart rate, respiratory rate, oxygen saturation, and blood pressure

d: Clinical laboratory parameters to be included: WBC, Hg, HCT, Plt, PT, PTT, BUN, serum creatinine, potassium, sodium, AST, ALT, total bilirubin, albumin, prealbumin, ESR, CRP, any blood, tissue, urine cultures as obtained per standard of care

e: Events of Special Interest include: gastrointestinal surgeries, sepsis, wound infection, urinary tract infection, feeding intolerance, transfusion requirements, phlebotomy complications

f: Adverse events related to study procedures (ie phlebotomy)

g: Complications will be assessed through the electronic medical record including excessive blood loss, transfusion requirements, injury to any organ system, infection in any organ system including wound bed, unanticipated return to the operating room, and any unexpected intra- or postoperative occurrence that requires medical or surgical attention

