6.3 Treatment Procedures

Operative Day (Day 1)

The following assessments will be conducted on the day the patient is administered the study drug and undergoes surgery.

- 1) Date, time, dose, route, and duration of metronidazole administration
- 2) Physical examination and vital signs, including weight, height, heart rate, respiratory rate, oxygen saturation and blood pressure, can be performed prior to intubation on the day of surgery
- 3) Laboratory determinations, if available, no blood draws will be performed just for the purposes of this study (See Section 6.6)
- 4) Concomitant medications of interest
- 5) Collection of PK plasma and intestine samples (including date/time; See Section 6.6.2)
- 6) Results for laboratory tests of interests (See Section 6.6.1)
- 7) Events of special interest (See Section 8.1)
- 8) Adverse events related to study procedures (See Section 8.4)
- 9) Information regarding the surgery performed including: type of surgery, laparoscopic vs. open procedure; times of incision, intestinal excision, closure; intubation, extubation; estimated blood loss, blood transfusions given, amount and type of intravenous fluids given
- 10) Intraoperative complications including: unexpected alteration in operative plan, excessive blood loss, need for transfusion, damage to any structure, conversion from laparoscopic to open procedure, death (See Section 8.2)

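### The Section 8.2 definition of an intraoperative complication conflicts with CLASSIC grade 1 in the same section and with the lists in 6.3 and Table 1 footnote g, so untreated deviations are likely to be under-recorded and coded inconsistently

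*Combined protocol and SAP*

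**What the plan says.** Four pieces of text decide which intraoperative events are recorded.

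- **Section 8.2, definition.** Complications are "instances where the anesthesia or surgical team alter treatment or surgical management to address an issue".
- **Section 8.2, capture and grading.** "All intraoperative complications documented by the anesthesia or surgical teams in the electronic medical record will be collected", and their severity is then classified on the CLASSIC scale. Grade 1 of that scale reads "Any deviation from the ideal intraoperative course without the need of any additional treatment or intervention". Grades 2 and 3 require added treatment or intervention, grade 4 is death, and grade 0 is the absence of any deviation.
- **Section 6.3, item 10.** On the operative day the study records intraoperative complications including "unexpected alteration in operative plan, excessive blood loss, need for transfusion, damage to any structure, conversion from laparoscopic to open procedure, death". The item ends with a cross-reference to Section 8.2.
- **Table 1 (Schedule of Study Procedures), footnote g.** Complications include "excessive blood loss, transfusion requirements, injury to any organ system", among others, and a catch-all: "any unexpected intra- or postoperative occurrence that requires medical or surgical attention".

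Section 16.1 requires complications to be graded, and Section 16.2 counts surgical outcome measures among the study data. The safety paragraph of Section 10.2 covers laboratory data, adverse events and events of special interest. It does not name complications, and it plans neither a complication rate nor a table by grade.

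**The concern.** The entry rule in 8.2 requires a response from the team. The lowest event grade on the scale it feeds describes a deviation that needed no added treatment. An abstractor who applies the rule first and the scale second will discard most grade 1 events before they can be graded. An abstractor who works from the list in 6.3 or from footnote g may keep some of the same events.

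What is at stake is the descriptive safety record. The grade distribution would depend on which section the abstractor followed, and its lowest event grade would be thin for a reason unrelated to how the operations went. With a planned 20 infants in two groups of 10 (Section 4.1, Table 2), a few events coded one way or the other would visibly change that distribution.

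**Working it through.** The documents state no figure to reproduce: they give no expected complication rate, threshold or grade distribution. The check is therefore a comparison of the texts, followed by one illustrative calculation.

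**Step 1. Run typical events through each rule.**

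| Event | 8.2 definition | 6.3 item 10 | Footnote g | CLASSIC grade by its wording |
|---|---|---|---|---|
| Minor structural or organ injury, nothing done | Out | In by the list, but refers back to 8.2 | In | 1 |
| Blood loss noted as excessive, nothing done | Out | In by the list, but refers back to 8.2 | In | 1 |
| Transient event that resolved by itself, on no list | Out | Not listed | Out: the catch-all needs medical or surgical attention | 1 |
| Operative plan changed, no treatment or intervention added | In | In | Depends on how the catch-all is read | 1 is possible |
| Deviation that needed added treatment | In | In if listed | In | 2 or higher |

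The first two rows are the direct conflict: in by the lists, out by the definition, and grade 1 by the scale. The third row shows events that the scale would grade but the 8.2 definition and the footnote's catch-all both leave out. The fourth row shows that grade 1 is not completely empty, because altering management is not the same thing as adding a treatment or intervention.

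**Step 2. Compare the parallel section.** Section 8.3 defines a postoperative complication by an alteration in the standard recovery pathway. Grade 1 of its Clavien-Dindo table is a deviation from postoperative care and expressly allows some minor measures. That definition and that scale fit together. The mismatch is confined to 8.2.

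**Step 3. Illustrate the size.** Let *p* be the share of infants whose only intraoperative event is an untreated deviation. The documents give no value, so I assume a range of 0% to 30%. Planned N = 20 (Section 4.1). If all such infants are left out under the literal 8.2 rule:

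- *p* = 0%: 0 × 20 = 0 infants uncounted
- *p* = 30%: 0.30 × 20 = 6 infants uncounted

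If abstractors record these events through the 6.3 list instead, the loss is smaller or nil. The range shows scale only; it is not an estimate.

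**The case against.** The strongest case on the other side has four parts.

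1. **Grade 1 is not unreachable.** A reader might infer that grade 1 must be zero by construction. The documents do not support that. A changed operative plan, which 6.3 lists, can meet the 8.2 definition without adding a treatment, and 6.3 and footnote g name blood loss and injury unconditionally. This objection stands and limits the claim to most untreated deviations.

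2. **The two conflicts pull against each other.** If the 6.3 list stands alone, untreated injuries are collected; if 8.2 governs it through the cross-reference, there is no separate conflict with 6.3. This is fair as logic, but the protocol does not say which reading applies. That is the ambiguity an abstractor faces, and on either reading 8.2 still disagrees with its own scale.

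3. **No planned result is wrong.** A reader might infer that the trial's complication rate will be understated. Section 10.2 plans no such rate, and a count of events with altered management would be correct under the 8.2 definition. It would be low only against a count of all CLASSIC grades 1 to 4. A reader might also infer that infants with only an untreated deviation will be reported as grade 0. Section 8.2 grades the complications that are collected and does not say how infants without one are reported. Both objections stand.

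4. **Materiality is low, and a changed-management threshold is workable for chart review.** This is a single-center, open-label PK study with drug given per routine care, and Section 8.1 captures transfusions and later gastrointestinal surgery separately. All of this is true, and it limits the importance of the point. It does not remove the mismatch: a threshold of changed management is a legitimate choice, but it does not fit a scale whose first event grade is untreated.

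**Conclusion.** The inconsistency is real and can be seen within Section 8.2 alone. Read literally, the definition keeps most untreated intraoperative deviations from being collected and graded. Grade 1 would then be under-recorded relative to the protocol's own scale, and the unconditional items in 6.3 and footnote g leave room for inconsistent coding of the same chart.

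The size cannot be derived from the documents. The illustration of 0 to 6 of 20 infants rests on an assumed 0% to 30% with only an untreated deviation and on the literal 8.2 rule being applied throughout; it shrinks to the extent that the 6.3 list captures the events. The finding does not extend to an empty grade 1 or to a biased complication rate.

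The effect is limited to descriptive safety data. The primary PK analysis and the sample size do not depend on it. It is still worth correcting, because Section 16.1 requires complications to be graded and the correction is small.

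**What to change.** - In Section 8.2, replace the definition with one that matches the scale: an intraoperative complication is any documented departure from the ideal course of the operation, that is, CLASSIC grade 1 or higher.
- Use the same definition in Section 6.3 item 10 and in Table 1 footnote g, with the named events given as examples and not as a separate rule.
- In Section 10.2, state that intraoperative complications will be summarized by CLASSIC grade.

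The definition itself is one sentence, with matching edits in the other places. The running cost is slightly more abstraction from anesthesia and operative notes. The change affects only what is recorded and graded; it does not alter patient care.

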8.3 Postoperative Complications

A postoperative complication will be limited to any issue arising after the patient leaves the operating room to 30 days after the operation. Postoperative complications are defined as any issue arising that

leads to alteration in the standard recovery pathway. All postoperative complications documented by the anesthesia or surgical teams in the electronic medical record will be collected and their severity will be classified using the Clavien-Dindo scale below¹⁵.

Clavien-Dindo Grade	Definition
Grade 0	Standard postoperative care without deviations from protocols
Grade 1	Any deviation from postoperative care without the need for pharmacologic, surgical, radiologic, or endoscopic interventions. (Allowed interventions – antiemetics, antipyretics, analgesics, diuretics, electrolytes, local wound care, and physiotherapy)
Grade 2	Requires pharmacologic treatment with drugs other than listed in grade 1, blood transfusions, or total parenteral nutrition
Grade 3	Requires surgical, endoscopic, or radiological intervention
Grade 4	Life-threatening complication with/ without intensive care unit management
Grade 5	Death

8.4 Adverse Events Related to Study Procedures

AEs and SAEs caused by the study specimen collections (e.g. bruising, bleeding) will be reported each time blood is collected for the study. No intestine will be removed for the purposes of the study and no surgery will be altered by participation in the study. AE information will be obtained by direct monitoring of the study subject by clinician observation by the care team, and self-reporting by the study subject or his/her guardian(s).

AEs related to study procedures will be followed until resolution or until 48 hours after study initiation or until discharge from the hospital, whichever comes first. Resolution of an AE is defined as the return to pretreatment status or stabilization of the condition with the expectation that it will remain chronic.

8.5 Follow Up of Events of Special Interest, Complications, and SAEs

All events of special interest, complications and AEs related to study procedures will be monitored through the electronic health record.

- The investigator is obligated to perform or arrange for the conduct of supplemental measurements and/or evaluations as medically indicated or as requested to elucidate the nature and/or causality of the event as fully as possible. This may include additional laboratory tests or investigations, histopathological examinations, or consultation with other health care professionals.
- New or updated information will be recorded in the originally completed CRF.
- The investigator will submit any updated event data within 24 hours of receipt of the information.

8.6 Reporting of Events of Special Interest, Complications, and AEs

Reporting will be completed via an Electronic Data Collection Tool

- The primary mechanism for reporting a complication, events of special interest, or AEs related to study procedures will be the electronic data collection tool in the protocol specific Duke RedCAP database.
- If the Duke RedCAP is unavailable, then the investigator will enter the complications, events of special interest, or AEs related to study procedures into the electronic system as soon as it becomes available.

9 CLINICAL MONITORING

This study does not provide intervention to the patient that has the potential to cause harm. Enrolled patients are receiving metronidazole as part of their treatment plan. However, the study will collect information regarding the presence of harmful clinical events that occur as a result of metronidazole infusion.

The electronic medical record will be searched for blood, urine, and tissue cultures in the postoperative period to monitor for infectious complications and noted in the CRF.

10 STATISTICAL CONSIDERATIONS

10.1 Sample Size Considerations

Sample size is derived to meet the primary objective of characterizing the PK of metronidazole in plasma and the intestinal wall of infants. As per FDA guidance, 20 infants will provide > 80% power to target a 95% confidence interval within 60% and 140% of the geometric mean estimates of metronidazole clearance and volume of distribution, assuming a coefficient of variation of up to 40%¹⁶. This will also provide >80% power to identify a 20% difference in plasma and intestinal wall concentrations of metronidazole and its primary metabolite 2-hydroxymetronidazole using a paired t-test at an alpha of 0.05. Because the study requires participation from the subject only during time of surgery, dropout rates should be low, and operative cancellations will be replaced.

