3.1.2 Secondary Outcome Measures

- 1) CYP2A6 quantification and other metabolizing and transporter enzymes
- 2) Ratios of metronidazole to 2-hydroxymetronidazole concentrations
- 3) Ratios of metronidazole in plasma/intestine
- 4) Ratios of 2-hydroxymetronidazole concentration in plasma/intestine

4 Study Design

Single center, open-label, non-randomized study to assess the intestinal pharmacokinetic profile of metronidazole in healthy children \leq 2 years of age undergoing elective intestinal operations for non-infectious conditions.

4.1 Number of Desired Participants:

A 20 infant sample size is derived to meet the primary objective of characterizing the PK of metronidazole in plasma and the intestinal wall of infants. Two desired gestational age ranges will be included in this study:

- < 34 weeks gestational age
- ≥ 34 weeks gestational age

[figure not shown]
All efforts will be made to approximately stratify enrollment as outlined in table 2.

Table 2 Age Stratification

Age	N = 20
< 34 weeks gestational age at birth	10
≥ 34 weeks gestational age at birth	10

Note: "Enrolled" means a participant's, or their legally acceptable representative's, agreement to participate in a clinical study after completion of the informed consent process. Potential participants who are screened for the purpose of determining eligibility for the study, but do not participate in the study, are not considered enrolled, unless otherwise specified by the protocol.

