Population PK analysis using non-linear mixed effects modeling (NONMEM VII software) will be used to estimate population PK parameters and their variance for both plasma and intestinal PK. The influence of covariates (i.e. postnatal age, gestational age, etc.) on PK parameters will be explored. Post-hoc Bayesian individual PK parameters will then be estimated for each subject. The plasma and intestinal concentrations-time profiles of metronidazole will be presented in figure form by subject and cohort as well as plasma to intestine concentration. Descriptive statistics will be presented for continuous and categorical variables. A detailed description of population PK analyses can be found in the PK analysis plan.

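### Does the claim of more than 80% power for a 20% plasma–intestine difference need correcting when no paired SD or scale is given?

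*Combined protocol and SAP*

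**What the plan says.** Section 10.1 derives the 20 infants from the primary objective: a 95% confidence interval within 60% to 140% of the geometric mean for "metronidazole clearance and volume of distribution, assuming a coefficient of variation of up to 40" per cent. A second sentence adds: "This will also provide >80% power to identify a 20% difference in plasma and intestinal wall concentrations of metronidazole and its primary metabolite". The metabolite meant is 2-hydroxymetronidazole, and the comparison is to be made "using a paired t-test at an alpha of 0.05".

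Section 3.1.2 lists the related secondary outcomes as "Ratios of metronidazole in plasma/intestine" and "Ratios of 2-hydroxymetronidazole concentration in plasma/intestine".

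The PK part of section 10.2 describes a population model and says that "profiles of metronidazole will be presented in figure form by subject and cohort as well as plasma to intestine concentration". It continues "Descriptive statistics will be presented for continuous and categorical variables" and then "A detailed description of population PK analyses can be found in the PK analysis plan". That PK analysis plan is not among the documents reviewed. Section 10.2 does not mention a paired t-test.

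**The concern.** The power of a paired t-test depends on the SD of the within-pair differences. Section 10.1 does not give that SD, or a correlation from which to derive it, for either analyte. Its only coefficient of variation belongs to clearance and volume of distribution, which are different quantities. Sidedness is also left open, and so is whether the 20% is a raw difference or a ratio. The analysis section then does not repeat the test.

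Two things could be at stake. The study might be less able to detect a 20% difference than the reader is told. And with the scale open, someone could choose between a raw-difference test and a log-ratio test after seeing the data, and the two do not always agree.

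**Working it through.** **Inputs from the plan (section 10.1):** 20 infants, so at most 20 pairs; a 20% difference; paired t-test; alpha 0.05 (taken as two-sided); power above 80%. **Not in the plan:** paired SD, correlation, scale. Values used for these below are assumptions.

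**1. The plan's own figure.** Power = P(|T| > t₀.₉₇₅,₁₉), where T is noncentral t with 19 degrees of freedom and noncentrality (δ/SD) × √20. Without an SD, this cannot be evaluated, so the stated figure can be neither reproduced nor refuted.

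**2. What the missing input must satisfy.** Solving for 80% power gives δ/SD = 0.660. Hence the largest SD that supports the claim is:
- raw scale: 0.20 / 0.660 = 0.303, about 30% of the mean;
- log scale, ratio 1.20: ln(1.20) / 0.660 = 0.182 / 0.660 = 0.276;
- log scale, ratio 0.80: 0.223 / 0.660 = 0.338.

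With fewer complete pairs the raw limit falls to 28.5% (18 pairs), 26.7% (16) and 20.1% (10).

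**3. In terms of correlation.** If both matrices have the same coefficient of variation (CV), SD = CV × √(2(1 − ρ)), so the ρ needed is 1 − (0.303/CV)²/2.
- CV 40%: 1 − (0.303/0.40)²/2 = 0.71.
- CV 30%: 1 − (0.303/0.30)²/2 = 0.49.

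Raw-scale power at an assumed CV of 40%:

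| ρ | 0 | 0.5 | 0.7 | 0.75 | 0.8 |
|---|---|---|---|---|---|
| Power | 32% | 56% | 78% | 85% | 92% |

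**4. On the log scale**, by assumed SD of log(tissue/plasma):

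| SD | Power, ratio 1.20 | Power, ratio 0.80 |
|---|---|---|
| 0.25 | 87% | 97% |
| 0.30 | 73% | 88% |
| 0.40 | 49% | 66% |
| 0.50 | 34% | 47% |

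The claim holds over part of a plausible range and fails over the rest.

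**5. Does the sample size depend on it?** For the precision claim, a CV of 40% is a log SD of √ln(1.16) = 0.385. With n = 20 the interval is exp(±2.093 × 0.385/√20), or about 0.84 to 1.20 times the geometric mean. That is well inside 0.60 to 1.40. In simulation nearly every trial met the target, so the reason given for 20 infants stands without the second sentence.

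**6. Does the scale matter?** I simulated 100,000 trials of 20 log-normal pairs, with the log-ratio test fixed at 80% power and an assumed 40% CV shared by both samples of an infant.

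| Noise in the log ratio | Raw-test power, ratio 1.20 | Raw-test power, ratio 0.80 |
|---|---|---|
| Half in tissue, half in plasma | 74% | 74% |
| 90% of variance in tissue | 83% | 60% |

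With noise split equally, the two tests disagree on significance in about 10% of trials. Neither scale is better in every setting. The result turns on the shared spread, the place of the noise and the direction of the difference, and the documents give none of these.

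**The case for a change.** The case for a change is that the gap is real and cheap to close. One reworded sentence in 10.1 could make the power conditional on a stated SD, and one line in 10.2 could fix a paired test on log(tissue/plasma). That would remove the choice of scale at no cost in infants or samples. Shared spread is likely because dosing is left to the treating physician (section 7.1.1) and excision times vary, so the scale is not a trivial matter. The unseen PK analysis plan is described as covering population PK, so it may not contain this test.

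The factual part of this stands. The paired SD, correlation, scale and sidedness are absent, and 10.2 omits the test. The pair count could also fall below 20, because 10.2 admits an infant with a single evaluable PK sample.

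The step from there to a required change does not stand:

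- Section 10.1 already names the comparison, both analytes, the test and alpha.
- Section 3.1.2 already names the ratios. A percentage difference with ratio outcomes reads naturally as a ratio, and the plan nowhere commits to raw differences.
- Section 10.2 provides 95% confidence intervals for continuous variables, although its examples are body measurements and not ratios.
- The gain claimed for a log-ratio test rests on assumed spreads and can reverse for a ratio of 1.20. The log ratio also removes dose and timing effects only if the tissue/plasma ratio does not itself depend on dose or sampling time.

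**Conclusion.** No change to the plan follows. The power sentence leaves out its key input, but it is not shown to be false. It is true if the paired SD is at most about 30% of the mean, or the SD of log(tissue/plasma) is at most 0.276 (ratio 1.20) or 0.338 (ratio 0.80). These limits assume 20 complete pairs and a two-sided alpha of 0.05. A within-infant correlation of about 0.71 at an assumed 40% CV would meet the raw-scale limit, and the documents neither support nor exclude that value.

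Nothing else hangs on the sentence. The number of infants comes from the precision target for clearance and volume, which is met comfortably. The comparison serves a secondary outcome in a single-centre, open-label PK study. What the data can say about a 20% difference will be read from the final confidence interval, whatever SD was assumed beforehand. An analyst working from the ratios in section 3.1.2 would be expected to report them with intervals and the number of pairs. This is a gap in documentation that ordinary practice fills. Readers should not quote the figure of more than 80% as an established property of the study.
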